6.3.2.3. Per-Protocol Population

The PP population includes all randomized participants who met all inclusion/exclusion criteria, are evaluable, adhered to the assigned study treatment regimen (as defined in Section 3.3.5), and returned to the study site for the TOC visit within the specified window (Visit 2 [Window: Day 15 -21]) and did not experience any of the following after enrollment:

- Unprotected vaginal sexual intercourse between Visit 1 and Visit 2

-
- New pregnancy reported by the subject
 - Receipt of any antibiotic or intravaginal microbicide other than study drug

In the unlikely event of an error in randomization or treatment administration (i.e., incorrect product), subjects will be grouped by the product they actually received.

6.3.3. Analysis Population Summaries

Table 5 summarizes the Safety and PP population eligibilities by actual treatment group and reasons excluded. Subjects will be included in the count for a particular reason for Exclusion if they met that criterion. As subjects may meet more than one criterion for exclusion, the “Excluded from...” counts may be less than the sum of the individual reason counts. A listing of the subjects excluded from each of the analysis populations and the reasons for exclusion will be provided (Listing 1). A listing of subjects whose assigned treatment group does not match their randomized treatment group will be provided in Listing 2.

6.4. Covariates and Subgroups

The protocol does not define any subgroup analyses for the primary and secondary efficacy analyses, while the exploratory efficacy analysis will be performed within subgroups defined by demographic and baseline characteristics of participants. Safety and enrollment summaries will be presented by clinical site.

6.5. Missing Data

Subjects who are not evaluable will be excluded from the PP population.

Participants who have a missing GV NAAT result at the TOC visit are excluded from the PP analyses. For the ITT population, participants who have a missing GV NAAT result at the TOC visit will be classified as treatment failures.

For ITT population, the Worst-Case imputation will also be explored. In this analysis, participants who have a missing GV NAAT result at the TOC visit in Amoxicillin arm will be classified as treatment failures while those who in placebo arm will be classified as cures.

Only GV eradication status will be imputed.

6.6. Interim Analyses and Data Monitoring

The study is monitored to determine if the following safety halting rule is met:

- 1) If any two participants experience an adverse event that is judged to be Severe (Grade 3) and related to treatment

If the halting rule is met, the study will not continue with the remaining enrollments or study treatments without a review by and recommendation from the DSMB to proceed. A summary of subjects meeting the halting rule is provided in Table 6. The DSMB may review study progress and participant safety data at study specific time frames, at least annually, as defined in the DSMB Charter. The halting rule does not utilize any statistical criteria and no formal hypothesis testing is planned to occur for the safety and enrollment data reviews.

6.7. Multicenter Studies

Safety and efficacy data will be pooled across all clinical sites. Center effects are not anticipated because treatment is self-administered, the sites are using standardized procedures for assessment of unsolicited adverse events, and the study relies on a central laboratory for Quantitative NAATs and Gram stain Nugent scoring.

6.8. Multiple Comparisons/Multiplicity

No adjustments for multiple testing are planned.

7. STUDY SUBJECTS

7.1. Disposition of Subjects

[Table 7](#) shows the number of subjects who are screen failures, the number of subjects that met each inclusion/exclusion criterion, and the number of subjects who were eligible but declined enrollment. The number of enrolled subjects in the study completing study milestones will be tabulated separately by randomized treatment group and all subjects. [Table 8](#) shows the total number of subjects screened, enrolled or randomized, treated, complying with treatment, and completing the TOC visit (Visit 2). A listing of subjects who completed the study, terminated early from study, or discontinued treatment and the reason for early termination or treatment discontinuation is included in [Listing 3](#).

[Figure 1](#) is a flowchart showing the disposition of study subjects in the safety and efficacy analyses, adapted from the CONSORT statement [1]. It shows the number of subjects eligible, enrolled and randomized, lost to follow-up, and analyzed for the safety, ITT and PP analyses by treatment group.

7.2. Protocol Deviations

A summary of subject-specific protocol deviations will be presented by the deviation category, the type of deviation, and randomized treatment group for all enrolled subjects ([Table 9](#)). All subject-specific protocol deviations and non-subject-specific protocol deviations will be included in Appendix 3 as data listings ([Listing 4](#) and [Listing 5](#), respectively).

8. EFFICACY EVALUATION

8.1. Primary Efficacy Analysis

The primary efficacy endpoint is the proportion of subjects with eradication of GV in each study arm at Visit 2 (Day 15-21) as assessed by NAAT. See Section 3.3.3 for the definition of eradication.

A test of hypothesis comparing the proportion of subjects with eradication of GV at Visit 2 (Day 15-21), will be conducted in the ITT population using the randomized treatment, and repeated as a secondary analysis using the actual treatment received in the PP population. The null hypothesis for each comparison is that there is no difference in proportions between treatment groups, with a two-sided alternative that considers the possibility of a difference in either direction. The test will be conducted using a Pearson Chi-Square test with Yates continuity correction at the 5% two-sided significance level. The number of subjects, the proportion of subjects with eradication of GV, and the 95% Wilson confidence interval for the proportion of subjects with eradication of GV will be presented for each analysis population and treatment group. In addition, the difference in proportions between the amoxicillin group and the placebo group and 95% Wilson confidence intervals will be presented. See Table 10 and Table 11. See Section 6.1 for pseudocode to fit the above analyses. Individual efficacy response data is presented in Listing 6.

8.2. Secondary Efficacy Analyses

There are no secondary efficacy objectives in this study.

8.3. Exploratory Efficacy Analyses

A summary of Amsel criteria is provided for subjects by visit and treatment group for each analysis population in Table 12 and Table 13. The number of Amsel criteria present (0,1,2,3), pH (> 4.5 , ≤ 4.5), Clue cells ($\geq 20\%$, $< 20\%$), and Amine ("whiff") test on KOH wet mount (Positive, Negative) will be summarized. A summary of Amsel criteria is provided for subjects by treatment group and GV eradication status at Visit 2 for subjects in the ITT population and PP population (Table 14 and Table 15). GV eradication status is categorized as "GV Eradicated," "GV Not Eradicated," "Not Evaluable." See Section 3.3 for the definition of evaluable. A subject listing of individual Amsel criteria will be provided in Listing 6.

Table 16 and Table 17 presents the proportion of subjects with Nugent score of 3 or less (normal), 4-6 (intermediate), and 7-10 (BV) in each treatment group at Screening and at Visit 2 (Day 15-21). Continuous Nugent scores will also be presented by analysis population, study visit, and treatment group in Table 18 and Table 19. A subject listing of Nugent scores will be presented in Listing 6. Raw Nugent scores are displayed graphically by visit, treatment group, and analysis population in Figure 2 and Figure 3. Categorical and Continuous Nugent Score characteristics at Visit 2 are presented by GV eradication status, and treatment group for subjects in the ITT population and PP population (Table 20, Table 21, Table 22 and Table 23).

The mean count of *Lactobacillus spp.*, *Gardnerella/Bacteroides spp.*, and *Mobiluncus spp.*, respectively, in each treatment group at Screening and at Visit 2 (Day 15-21). Mean count and standard deviation of each specimen type will be presented by study visit, analysis population, and treatment group. Additionally, mean change from baseline and corresponding standard deviation will be presented for Visit 2. See Table 24 and Table 25. Mean count and standard deviation of *Lactobacillus spp.*, *Gardnerella/Bacteroides spp.*, and *Mobiluncus spp.* at Visit 2 is presented by GV eradication status for subjects in the ITT population and PP population (Table 26 and Table 27).

The exploratory outcome measure is the demographic and behavioral factors among women in the NAAT screening population without vaginitis who are baseline GV positive and women who are baseline GV negative. Gender, ethnicity, and race will be summarized by baseline GV status for subjects in the NAAT screening population in [Table 28](#). Age will be summarized by baseline GV status in [Table 29](#). Baseline GV status will be “Positive” or “Negative” as determined by NAAT at the screening visit.

Categorical and continuous sexual history questions will be summarized by baseline GV status ([Table 30](#), [Table 31](#)) and by treatment group at baseline and Visit 2 BV status, respectively ([Table 32](#), [Table 33](#), [Table 34](#), and [Table 35](#))

Additionally, the demographic and baseline characteristics of participants who were positive for BV by Nugent Score and Amsel Criteria and by treatment group at Visit 2 (Day 15-21) will be summarized. See [Table 36](#), [Table 37](#), [Table 38](#) and [Table 39](#).

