11.4.4.2 Exploratory Efficacy Analysis

Details of the exploratory efficacy analysis, as well as any additional exploratory analyses that may be performed to supplement the primary analysis, will be described in the separate Statistical Analysis Plan. As an example of the latter, demographic and baseline characteristics of participants who received amoxicillin and were positive for BV by Nugent Score and Amsel Criteria at Visit 2 (Day 15-21) will be summarized.

DATA/DOCUMENTS

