3. STUDY OBJECTIVES AND ENDPOINTS

3.1. Study Objectives

Primary Objective:

- To determine if treatment with amoxicillin eradicates GV in women who are colonized/infected with GV but have no clinical evidence of BV.

Secondary Objective:

- To evaluate the safety and tolerability of amoxicillin compared to placebo.

Exploratory Objectives:

- To determine the demographic and behavioral factors associated with vaginal colonization of GV.

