3.2. Endpoints

Primary Endpoint:

- The proportion of participants with eradication of GV in each study arm at Visit 2 (Day 15-21) as assessed by nucleic acid amplification test (NAAT).

Secondary Endpoint:

- The proportion of participants reporting related adverse events (AEs) and serious adverse events (SAEs) in each study arm following the first dose of study product through Visit 2 (Day 15-21).

Exploratory Endpoint:

- The demographic and behavioral factors among women in the NAAT screening population without vaginitis who are baseline GV positive and women who are baseline GV negative.

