4. INVESTIGATIONAL PLAN

4.1. Overall Study Design and Plan

This is a randomized, double-blind, placebo-controlled Phase 2 study screening approximately 245 adult females 18-45 years of age to enroll approximately 98 participants to achieve 82 evaluable participants at the test of cure (TOC) visit. The study is designed to determine if amoxicillin will eradicate vaginal colonization/infection with GV when administered to women who are colonized/infected with GV but have no clinical evidence of BV. Women who consent to screening participation undergo pelvic examination on entry and vaginal specimens collected for pH, whiff test and wet prep microscopy (Amsel criteria with the exception of evaluation of vaginal discharge), Nugent score, NAAT for trichomonas, and quantitative NAAT for GV. At Visit 1 (Enrollment - Day 1) women who tested positive for GV by NAAT, negative for BV by Nugent and negative for trichomonas by NAAT are enrolled and randomized to one of two groups (amoxicillin or placebo). A TOC is completed at Visit 2 (Day 15-21).

Baseline information is collected from all women at the screening visit (Visit 0 (Day -14 to -7)). This information consists of demographics, medical and sexual history, concomitant medications, and clinical and laboratory findings. Vaginal swabs are collected as noted above. Women who test positive for vaginitis at the screening visit are screen failures. At the Enrollment Visit (Visit 1, Day 1) women who tested positive for GV, negative for abnormal flora/BV, and negative for trichomonas are enrolled and randomized. Those who were negative for GV are screen failures and do not continue in the study, but, their, demographic, medical, and sexual history as well as baseline swabs are used for comparisons to the GV positive women for an exploratory objective.

Women who are enrolled are asked to return for one further visit, Visit 2 (Day 15-21), where a TOC is completed (a pelvic exam completed with the same specimens taken as those at baseline with the exception of the trichomonas NAAT).

Participants are queried regarding any adverse outcomes and all AEs will be collected through Visit 2. Laboratory testing includes (NAAT for trichomonas; Nugent score for BV; quantitative NAAT for GV; and assessment of vaginal pH, saline microscopy (yeast, trichomonas, clue cells).

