6.1.1. Pseudo Code

The following SAS® pseudo code will be used to calculate the following:

Chi-Square test at 5% two-sided significance level and odds ratio (and 95% asymptotic CI) from 2x2 table:

```
proc freq;
  Table treatment*analysis_variable / chisq;
  ods output ChiSq=outputdsn1;
  ods output RelativeRisks=outputdsn2;
run;
```

Note: Yates continuity correction is where Statistic = "Continuity Adj. Chi-Square";

Fisher's Exact test at 5% two-sided significance level:

```
proc freq;
  Table treatment*analysis_variable / exact;
  ods output FishersExact=outputdsn;
run;
```

95% Wilson CI for proportions/percentages:

```
proc freq;
  Table treatment*analysisvariable / binomial(wilson);
  ods output binomialcls=outputdsn;
run;
```

95% Wilson CI for difference in proportions (produces Newcombe CI):

```
proc freq;
  Table treatment*analysisvariable / riskdiff(cl=Wilson);
  Exact Riskdiff;
  ods output pdiffcls=outputdsn;
run;
```

95% Exact Blaker CI for proportions/percentages:

```
proc freq;
  Table treatment*analysisvariable / binomial(blaker);
  ods output binomialcls=outputdsn;
run;
```

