		GV Eradicated (N = X)	GV Not Eradicated (N = X)	Not Evaluable (N = X)	GV Eradicated (N = X)	GV Not Eradicated (N = X)	Not Evaluable (N = X)	GV Eradicated (N = X)	GV Not Eradicated (N = X)	Not Evaluable (N = X)
Lactobacillus spp.	Mean	x.x	x.x	x.x	x.x	x.x	x.x	x.x	x.x	x.x
	Standard Deviation of Mean	x.x	x.x	x.x	x.x	x.x	x.x	x.x	x.x	x.x
Gardnerella/Bacteroides spp	Mean	x.x	x.x	x.x	x.x	x.x	x.x	x.x	x.x	x.x
	Standard Deviation of Mean	x.x	x.x	x.x	x.x	x.x	x.x	x.x	x.x	x.x
Mobiluncus spp	Mean	x.x	x.x	x.x	x.x	x.x	x.x	x.x	x.x	x.x
	Standard Deviation of Mean	x.x	x.x	x.x	x.x	x.x	x.x	x.x	x.x	x.x

Treatment group is the treatment to which the subject was randomized.

Tables with similar format:

Table 27: Mean count of *Lactobacillus spp.*, *Gardnerella/Bacteroides spp.*, and *Mobiluncus spp.* At Visit 2 by GV Eradication Status and Treatment Group - PP Population

Implementation Note:

1. Change footnote from “Treatment group is the treatment to which the subject was randomized.” to “Treatment group is the actual treatment received.”
2. No “Not Evaluable” Column for PP Population.

Table 28: Summary of Categorical Demographic and Baseline Characteristics by GV Status at Screening - NAAT Screening Population

Variable	Characteristic	GV Positive (N=X)		GV Negative (N=X)	
		n	%	n	%
Sex	Female	x	XX	x	XX
Ethnicity	Not Hispanic or Latino	x	XX	x	XX
	Hispanic or Latino	x	XX	x	XX
	Not Reported	x	XX	x	XX
	Unknown	x	XX	x	XX
Race	American Indian or Alaska Native	x	XX	x	XX
	Asian	x	XX	x	XX
	Native Hawaiian or Other Pacific Islander	x	XX	x	XX
	Black or African American	x	XX	x	XX
	White	x	XX	x	XX
	Multi-Racial	x	XX	x	XX
	Unknown	x	XX	x	XX

N=Number of Subjects in the GV NAAT population within the specified GV status category.

Table 29: Summary of Continuous Demographic and Baseline Characteristics by GV Status at Screening – NAAT Screening Population

Variable	Statistic	GV Positive (N=X)	GV Negative (N=X)
Age	Mean	x.x	x.x
	Standard Deviation	x.x	x.x
	Median	x.x	x.x
	Minimum	x	x
	Maximum	x	x

N=Number of Subjects in the GV NAAT population within the specified GV status category.

Table 30: Categorical Baseline Sexual History by GV Status at Screening - NAAT Screening Population

Sexual Behavior Category	Value	GV Positive (N=X)		GV Negative (N=X)	
		n	%	n	%
Has the subject ever douched or used vaginal preparations or drying agents?	No	x	x	x	x
	Summer’s Eve	x	x	x	x
	Rephresh	x	x	x	x
	Vagisil	x	x	x	x
	Other	x	x	x	x

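### The exploratory objective asks which factors are associated with GV colonization, but SAP Tables 28-31 plan only side-by-side summaries, with no measure of association, no interval and no stated restriction to women without vaginitis.

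*SAP*

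**What the plan says.** SAP 3.1 gives the exploratory objective: "To determine the demographic and behavioral factors associated with vaginal colonization of GV". SAP 3.2 turns it into an endpoint: "The demographic and behavioral factors among women in the NAAT screening population without vaginitis who are baseline GV positive", set beside those who are GV negative. SAP 4.1, like Protocol section 4, says that the GV-negative screen failures' histories and "baseline swabs are used for comparisons to the GV positive women for an exploratory objective".

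Protocol 11.4.4.2 leaves the method to the SAP: "Details of the exploratory efficacy analysis, as well as any additional exploratory analyses" are to be described there. SAP 8.3 then plans that "Gender, ethnicity, and race will be summarized by baseline GV status for subjects in the NAAT screening population in" Table 28, that age is summarized in Table 29, and that "Categorical and continuous sexual history questions will be summarized by baseline GV status" in Tables 30 and 31.

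The shells have one column group for GV-positive and one for GV-negative women. Categorical items show n and %. Continuous items show mean, SD, median, minimum and maximum. The footnote under Tables 28-30 defines the column total: "N=Number of Subjects in the GV NAAT population within the specified GV status category". SAP 6.3.2.2 defines the NAAT Screening population as all screened women evaluated for GV by NAAT.

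**The concern.** An objective about association needs a contrast between the groups and some statement of its precision. The plan stops one step earlier, at two columns of summaries. A reader of the clinical study report would see, for example, 50% against 40% and have to judge unaided whether that gap means anything. If estimates are added only after the data are seen, the choice of which factors to report will no longer be pre-specified.

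The population is a second gap. The endpoint covers women without vaginitis, but neither the population definition nor the table shells carry that restriction. The Protocol's background section says that GV is found in nearly all women with BV. If women with an abnormal Nugent score stay in the tables, a factor related to BV could therefore look like a factor related to GV.

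**Working it through.** **1. Is a contrast or interval planned anywhere else?**
- SAP 6.1 provides Wilson intervals for efficacy variables, and tests that compare treatment groups. SAP 4.5 ties the efficacy variables to eradication, Amsel criteria and Nugent score. None of this is GV-positive against GV-negative.
- SAP 6.1.1 has code for "Chi-Square test at 5% two-sided significance level and odds ratio (and 95% asymptotic CI) from 2x2 table", but it crosses treatment with an analysis variable. No table shell prints an odds ratio.
- SAP 6.4 says that the exploratory analysis is done within demographic and baseline subgroups, but names no estimate.
- SAP 12 plans no further analyses.

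So no measure of association is assigned to this comparison.

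**2. Who can enter the tables?** Under Protocol 7.1, a woman with yeast, trichomonas or abnormal flora on on-site microscopy has her remaining specimens discarded, so she should have no GV NAAT. The same section describes women who are GV positive by NAAT and also test positive for BV or trichomonas afterwards. They are ineligible for randomization, but they meet the NAAT Screening definition. Their number is not given.

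**3. Group sizes.** The plan gives no figure for this comparison, so they come from its sample-size section. 41/0.85 = 48.2, rounded up to 49 per arm, gives 98 randomized. 98/0.40 = 245 screened. Both match the plan. The remainder is 245 − 98 = 147 GV-negative women. This split treats every GV-positive woman without BV as randomized.

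**4. Precision of the missing estimates.** Factor prevalence p is not in the documents, so 10% to 50% is assumed, equal in both groups:
- SE(log OR) = √[1/(98p) + 1/(98(1−p)) + 1/(147p) + 1/(147(1−p))]
- 95% CI factor = exp(1.96 × SE)
- half-width for a difference in proportions = 1.96 × √[p(1−p)(1/98 + 1/147)]

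The last column takes p as the prevalence in GV-negative women and gives the odds ratio detectable with 80% power at two-sided 5% (normal approximation).

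| p | SE(log OR) | CI factor | Half-width (points) | Detectable OR |
|---|---|---|---|---|
| 10% | 0.435 | 2.34 | 7.7 | 2.75 |
| 20% | 0.326 | 1.89 | 10.2 | 2.27 |
| 30% | 0.285 | 1.75 | 11.7 | 2.13 |
| 50% | 0.261 | 1.67 | 12.8 | 2.12 |

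For a continuous factor, the half-width of a mean difference is 1.96 × √(1/98 + 1/147) = 0.26 SD.

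**5. Worked example.** Suppose that 49 of 98 GV-positive and 59 of 147 GV-negative women have a factor. The planned table prints 50% and 40%.
- OR = (49 × 88)/(59 × 49) = 1.49
- SE = √(1/49 + 1/49 + 1/59 + 1/88) = 0.263
- 95% CI: 0.89 to 2.50
- Difference: 9.9 points (Newcombe 95% CI −2.8 to 22.2)

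The data are compatible with no association, and the planned table does not show that.

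**The case against.** The strongest reply is that the endpoint is descriptive. It names the factors in two groups of women and no difference or ratio, and Protocol 11.1 plans a single formal test, for the primary outcome. Descriptive reporting of an exploratory objective in a Phase 2 trial is defensible. This stands as a reason not to ask for p-values. It does not remove the mismatch with an objective about association and a design section that speaks of comparisons.

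A reader might infer that no association could be stated at all. The tables do not support that. Counts give a crude odds ratio and its interval, as in the example above, and mean, SD and N give a mean difference. What is absent is a planned and printed estimate with its uncertainty.

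A reader might also infer that the SAP already holds the right tool and forgot to use it. The odds-ratio code is written for treatment comparisons, so it shows no such intent.

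Nor do the documents show that the GV-positive column will be dominated by women with BV. On-site screening removes women with visible vaginitis before the NAAT, and the opening sentence of the relevant paragraph in SAP 8.3 repeats the endpoint's restriction, so the exclusion may be intended. It is simply not carried into the population definition or the shells.

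Finally, precision is not uniformly good. For a factor with 10% prevalence, only an odds ratio of about 2.75 would be detected with 80% power. That argues for printing the interval.

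**Conclusion.** The point holds as a minor one. The objective and design call for a comparison of GV-positive with GV-negative women. The planned output is summaries by group, with no measure of association or precision and no stated vaginitis restriction. With about 98 and 147 women, the missing odds ratios would be known to within a factor of about 2.3 at 10% prevalence and 1.7 at 50%. This rests on the plan's 40% GV-positive rate and on assumed prevalences. How many women with late-detected vaginitis would enter the tables cannot be worked out from the documents. The primary and safety conclusions do not depend on any of this.

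**What to change.** In SAP 8.3 and Tables 28-31:
- State that the tables include only women without vaginitis, meaning negative on on-site microscopy, Nugent score 0-3 and negative trichomonas NAAT.
- For each categorical factor, add a crude odds ratio, or a difference in proportions, with a 95% CI. For condom use, keep the denominator already in the Table 30 footnote (women with male partners in the time frame). Collapse sparse race categories by a rule set in advance. The sex row needs no estimate, since every participant is female.
- For each continuous factor, add a mean difference, or an odds ratio per unit, with a 95% CI.
- Label all of these as exploratory and not adjusted for multiplicity.

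The cost is extra columns and a population filter, using data already collected. The downside is several unadjusted intervals, some of which may exclude no association by chance. An adjusted logistic model is optional. It would need choices about covariates and category collapsing that the documents do not settle. If the sponsor prefers description only, rewording the objective would remove the first mismatch, but the vaginitis restriction would still have to be stated.
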